Tumor assessments will be performed at screening and approximately every 8 weeks starting at the end of cycle 2 for the first 6 months (cycles 2, 4, 6) and then every 12 weeks (cycles 9, 12, 15, etc.), or sooner if deemed necessary by the Investigator, and will continue until disease progression. A tumor assessment will be performed upon treatment discontinuation (End of Treatment visit) if the reason for discontinuation is other than disease progression and no tumor assessment was performed in the prior 8 weeks, or a tumor assessment is required for the confirmation of response to treatment. Subjects who discontinue treatment for reasons other than disease progression must continue tumor assessments until disease progression, withdrawal of subject's consent or initiation of another anticancer therapy. Determination of objective tumor response will be performed by the Investigator. However, tumor images may be de-identified of subject's personal information at the clinical sites and collected by the Sponsor or designee to undergo an external independent radiological review if the sponsor deems it necessary for the final assessment of the efficacy of the treatment. If an independent radiological review were to be conducted, reviewers would be blinded to Investigator's tumor response assessments. An independent review committee charter would be generated to provide the specific procedures that would be filed with IRB/ECs and regulatory authorities.

Subjects with a solitary site of disease who have experienced a response may be considered for surgical resection. Subjects with a Partial Response (PR) and residual disease after salvage surgery are eligible to continue on study therapy.

Upon disease progression, all subjects in the study cohort will be followed approximately every 12 weeks for survival and the use of subsequent therapy until either death or 12 months after accrual in the subject's study cohort has been completed, whichever occurs first. Information on survival and subsequent anticancer therapy may be collected by phone.

All subjects will be followed-up for safety during treatment and up to approximately 30 days (30 +/- 7 days) after treatment discontinuation or until immediately before the initiation of another anti-cancer therapy, whichever occurs first. Additional follow up may be implemented until the

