8.4 Removal of Subjects from Treatment or Assessment

Subjects may withdraw their consent to participate in this study at any time without prejudice. The Investigator must withdraw from the study any subject who requests to be withdrawn. A subject's participation in the study may also be discontinued at any time at the discretion of the Investigator and in accordance with his/her clinical judgment. Every effort should be made to complete, whenever possible, the tests and evaluations listed for the End of Treatment visit. The Sponsor must be notified of all subject withdrawals as soon as possible. The Sponsor also reserves the right to discontinue the study at any time for either clinical research or administrative reasons and to discontinue participation by an individual Investigator or site for poor enrolment or noncompliance.

Overall, the reasons for which the Investigator or Kura Oncology may withdraw a subject from study treatment include, but are not limited to, the following:

- Subject experiences disease progression
- Subject experiences unacceptable toxicity
- Subject experiences toxicity that is deemed by the Investigator to be no longer safe for the subject to continue therapy
- Subject requests to withdraw from the study treatment
- Subject requires or has taken medication prohibited by the protocol
- Subject is unwilling or unable to comply with the study requirements
- Subject withdraws consent to collect health information
- Subject was erroneously admitted into the study or does not meet entry criteria

- Subject is lost to follow-up
- Subject becomes pregnant

Subjects will return for an End of Treatment visit within approximately 30 days after the last administration of the study drug (or sooner if another anticancer therapy is to be initiated). If a subject fails to return for scheduled visits, a documented effort must be made to determine the reason. If the subject cannot be reached by telephone after 2 attempts, a certified letter should be sent to the subject (or the subject's legally authorized representative, if appropriate) requesting contact with the Investigator. This information should be recorded in the study records.

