9.2 Treatment Administration

Tipifarnib will be administered with food at a starting dose of 600 mg, po, bid daily on days 1-7 and 15-21 of 28-day treatment cycles.

The first study dosing (Cycle 1 Day 1) will take place in the study clinic. Tipifarnib will be administered orally with a meal in the morning and again approximately 12 hours later at approximately the same times each treatment day. Tablets should be swallowed whole with water (~8 oz. or 250 mL) but may be chewed or crushed if the Investigator deems it necessary. Use of percutaneous endoscopic gastrostomy tubes is allowed at the judgment of the Investigator. If a dose is vomited or partially vomited, it should not be replaced with a new dose.

Subjects may use proton pump inhibitors or H2 antagonists during the treatment portion of this study. However, subjects should be instructed to use antacids (magnesium or aluminum containing products) at least 2 hours before or after intake of oral study drug.

On Cycle 1 Day 1, the site will provide tipifarnib to the subject from bulk supplies. Subjects will be provided with diaries with instructions to record the date and time of each dose and asked to bring the diaries and tablet bottles to each clinic visit for subject compliance and drug accountability review by the site staff.

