9.12 Non-permitted Treatments

Use of the following medications and therapies is not allowed during the trial:

- Investigational agents other than tipifarnib.
- Any other anticancer therapy, including radiation or surgery, for the primary disease
 under study with the exceptions of palliative treatment of non-target lesions and treatment
 of residual disease in study subjects who have experienced a partial response during the
 study.
- High dose systemic corticosteroids or any other immunosuppressive drugs except:
 - o Glucocorticosteroid treatment administered with a daily dose of \leq 20 mg prednisone or equivalent,
 - Single doses for the management of treatment-related AEs or for premedication of BSC agents.

- Sensitive substrates of CYP3A4 beginning Cycle 1 Day 1 and during the subject's participation in the tipifarnib treatment portion of this study.
 If continued concomitant therapy is needed, subjects should be transitioned to a medicine that is not a sensitive substrate of CYP3A4.
- Subjects should not use enzyme-inducing anti-convulsants (e.g. phenytoin, phenobarbital, and carbamazepine) while taking tipifarnib. If needed, subjects may use non-enzyme-inducing anti-convulsants (e.g. gabapentin, topiramate, valproate) while taking tipifarnib.

If the administration of a non-permitted concomitant drug becomes necessary during the trial, e.g., because of AEs or disease progression, the subject in question will be withdrawn from the trial, and the subject's data which will have been obtained before the withdrawal may be used for safety and efficacy evaluations.

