11.6 End of Treatment Visit

The following assessments will occur approximately 30 days (+/- 7 days) after the last administration of study drug or immediately before the administration of another anti-cancer drug, whichever takes place first:

- Physical examination
- Record subject weight and vital signs (blood pressure, pulse, temperature)
- ECOG performance status.
- Hematology
- Chemistry (fasting not required)
- Serum/urine pregnancy test for females of child-bearing potential only
- Tumor radiological assessments for subjects who have not previously demonstrated disease progression in the study unless completed within the previous 4 weeks. Tumor assessments may also be undertaken for a confirmation of objective response.
 - o CT scan with a contrast agent is the preferred imaging method and the same technique should be used at baseline and post-treatment assessments.
 - In subjects with HNSCC, CT scan coverage at screening should encompass scans
 of the neck (including the skull base), chest and abdomen (including the liver and
 adrenals). Any other areas of disease involvement should be scanned based on
 the subject's signs and symptoms.
 - o In subjects with other solid tumors, scan coverage should be appropriate to ensure that all areas of disease involvement are scanned.
- Assessments of adverse event and concomitant medications.
- Conduct drug accountability on the returned empty bottles and unused medications.

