11.7 Post Treatment Follow up

Follow up visit(s) are required only for subjects who terminated treatment for reasons other than death or disease progression and should occur approximately every 8-12 weeks until disease progression or death, whichever occurs first. If the subject initiates a new anticancer therapy without evidence of disease progression by RECIST v1.1, tumor assessments should continue

until there is evidence of disease progression unless withdrawal of subject's consent to study procedures.

The assessments to be conducted at these visits are:

- Radiographic Imaging: to be performed if not done within the prior 8 weeks or if a tumor assessment is required for the confirmation of response.
 - o CT scan with a contrast agent is the preferred imaging method and the same technique should be used at baseline and post-treatment assessments.
 - o In subjects with HNSCC, CT scan coverage at screening should encompass scans of the neck (including the skull base), chest and abdomen (including the liver and adrenals). Any other areas of disease involvement should be scanned based on the subject's signs and symptoms.
 - o In subjects with other solid tumors, scan coverage should be appropriate to ensure that all areas of disease involvement are scanned.
- Assessments of AEs and concomitant medications may also be conducted if AEs were not resolved at the time of the End of Treatment visit.

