6. ANALYSIS POPULATIONS

Enrolled subjects are those that signed informed consent and either met all inclusion and exclusion criteria or were authorized by Sponsor to receive study drug treatment.

Full analysis set (FAS)

The FAS population will serve as the primary population for the analysis of tumor response and other efficacy-related data. Subjects will be excluded from FAS for the following reasons:

- No baseline data
- Failure to receive at least one dose of tipifarnib
- No evaluable post-baseline endpoint data subsequent to at least 1 dose of study drug
- If the only post-baseline assessment is Stable Disease and it occurred prior to 6 weeks from first dose.

Protocol KO-TIP-001

Subjects will be grouped in the FAS population according to cohort as described in Section 4.1.

Per-Protocol (PP) Population

A supportive analysis using the PP population will be performed for the tumor response analysis. The PP population excludes subjects due to major deviations from the protocol that may substantially affect the results of the primary analysis. The final determination on protocol violations, and thereby the composition of the PP population, will be made prior to locking the clinical database and final analysis and will be documented in a separate memorandum.

All Subjects as Treated (ASaT) population

The ASaT population will be used for the analysis of safety data. The ASaT population consists of all enrolled subjects who receive at least one dose of tipifarnib. At least one laboratory or vital sign measurement obtained subsequent to at least one dose of study drug is required for inclusion in the analysis of a specific safety parameter. To assess change from baseline, a baseline measurement is also required.

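### Protocol 9.12 removes a subject who needs a non-permitted drug from the trial, while 8.4 and 8.1 stop only tipifarnib and keep scanning: a narrow conflict that can cost PFS and DOR data

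*Protocol*

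**What the plan says.** Protocol 9.12 lists the drugs not allowed on study. If one becomes necessary, for example because of an adverse event or progression, then "the subject in question will be withdrawn from the trial". It adds that data obtained before the withdrawal may be used, and is silent on later data.

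Protocol 8.4 gives the same trigger, "Subject requires or has taken medication prohibited by the protocol", in a list of reasons for which the Investigator or Sponsor "may withdraw a subject from study treatment".

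Protocol 8.1 says: "Subjects who discontinue treatment for reasons other than disease progression must continue tumor assessments until disease progression". The only other end points it allows are consent withdrawal and another anticancer therapy. Protocol 10.1 and SAP 4.1 say the same. Protocol 11.7 adds: "Follow up visit(s) are required only for subjects who terminated treatment for reasons other than death or disease progression". Those visits come about every 8 to 12 weeks.

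SAP 9.2 uses scans made after treatment discontinuation for PFS. It censors DOR at the analysis cutoff date for a responder who is alive without documented progression.

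**The concern.** The sections disagree on force (mandatory in 9.12, discretionary in 8.4) and on scope (the trial or only the drug). A site that follows 9.12 as written stops scanning a subject whom 8.1 says must still be scanned. The reason for stopping, such as an adverse event that needs sustained steroids, may be related to outcome.

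The consequences would be:

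- **PFS** is censored at the last scan instead of running to a later progression. SAP 9.2 also counts a death within 126 days of the last scan as an event, and that death may go unrecorded once follow-up has ended.
- **Response** may go unconfirmed, or a later first response may go unseen.
- **DOR** may be credited with time that no scan supports.
- **FAS membership** of an early leaver may depend on which End of Treatment scan rule the site applies.

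**Working it through.** The plan gives no figure on this point, so the check compares the texts and then works through the calendar.

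**1. The rules side by side**

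| Place | Force | What ends | Scans afterward |
|---|---|---|---|
| Protocol 9.12 | mandatory | participation in the trial | none provided for |
| Protocol 8.4 | discretionary | study treatment | not addressed, apart from the End of Treatment visit |
| Protocol 8.1, 10.1; SAP 4.1 | mandatory | treatment already stopped, no progression | until progression, consent withdrawal or another anticancer therapy |
| Protocol 11.7 | required | treatment already stopped, no progression | about every 8-12 weeks, even after a new anticancer therapy |

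No text reconciles the first row with the others.

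**2. Who is affected**

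- *New anticancer therapy:* 8.1 itself ends scans and SAP 9.2 censors DOR. Only 11.7 would continue.
- *Drug needed after documented progression:* the PFS or DOR event has already occurred.
- *Sensitive CYP3A4 substrates and enzyme-inducing anticonvulsants:* 9.12 bars these only during tipifarnib treatment and points to alternatives.
- *What remains:* mainly steroids above 20 mg/day prednisone equivalent beyond single doses, or other immunosuppressants, in a subject without progression.

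**3. Scan calendar**

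Day = (cycle - 1) x 28 + 22. Cycle 2 gives Day 50, Cycle 4 Day 106, Cycle 6 Day 162 and Cycle 9 Day 246.

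**4. DOR and PFS in one illustrative subject**

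Assume first PR on Day 50, last dose on Day 49, End of Treatment scan on Day 79 (last dose + 30), and progression that the Day 162 scan would show. Months = days / 30.4375 (SAP 7.1).

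- DOR under 8.1: event at 162 - 50 = 112 days (3.7 months).
- Scan-supported DOR under 9.12: 79 - 50 = 29 days (1.0 month).
- DOR under 9.12 with SAP 9.2 cutoff censoring, subject recorded as alive: 365 - 50 = 315 days (10.3 months) for an assumed cutoff at Day 365; 730 - 50 = 680 days (22.3 months) for Day 730.
- PFS from first dose: event at 162 - 1 = 161 days (5.3 months) under 8.1; censored at 79 - 1 = 78 days (2.6 months) under 9.12.

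**5. FAS membership of a Cycle 1 leaver**

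Dosing is "bid daily on days 1-7 and 15-21 of 28-day treatment cycles", so the last dose in Cycle 1 falls on Days 1-7 or 15-21. The End of Treatment visit (nominally + 30) is then on Days 31-37 or 45-51. SAP 6 excludes a subject without evaluable post-baseline data, and also: "If the only post-baseline assessment is Stable Disease and it occurred prior to 6 weeks from first dose". Six weeks from first dose is Day 43.

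Whether that visit includes a scan depends on the section:

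- Protocol 11.6 requires one in a subject without progression "unless completed within the previous 4 weeks".
- Protocol 8.1, 10.1, Table 1 note 9 and SAP 4.1 use 8 weeks (56 days), with an exception for confirming a response.

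Take a last dose on Day 7, so a visit on Day 37. A screening scan made s days before Day 1 (s = 1 to 28) is then 36 + s = 37 to 64 days old. The 4-week rule always calls for a new scan. The 8-week rule does not for s = 1 to 20, that is, 20 of the 28 possible days.

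Under 9.12 this leaver therefore has either no post-baseline scan or one on Day 37. Stable disease on Day 37 alone also means exclusion from the FAS. Under 8.1 the Day 50 scan follows in either case. For a last dose on Days 15-21, a scan at the visit falls after Day 43 and the subject stays in, if a scan is made.

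**The case against.** The strongest reply is that a sensible site would reconcile the sections. The continue-scanning sentence stands in several places and allows only three end points, and a prohibited concomitant drug is not one of them. Section 8.4 attaches this trigger to treatment. Loss of scans is thus possible, not established. This stands, and it limits the weight of the point. It does not remove the conflict, because 9.12 is the section a site opens when the situation arises, and its wording is mandatory.

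A reader might infer three stronger things that the documents do not support:

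- *DOR will be overstated.* Cutoff censoring applies only to a subject recorded as alive, which is uncertain for someone out of the trial. SAP 7.6 censors dropouts but gives no date, so another reading is open. The cutoff rule is also a weakness of the SAP in its own right: it affects any responder who stops being scanned, whatever the cause.
- *The two-stage test or the ORR is materially biased.* That would need an unscanned subject and a replacement that 8.2 leaves to discretion. Section 8.2 does not plainly cover a subject with early stable disease. End of Treatment scans to confirm a response are also provided for.
- *Every Cycle 1 leaver is scanned at End of Treatment.* That holds only under the 4-week rule in 11.6.

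**Conclusion.** The conflict is real and nothing in the documents resolves it. It is narrow, reaching mainly a subject without progression who needs sustained higher-dose steroids or another immunosuppressant. For that subject, following 9.12 loses later scans and survival follow-up. PFS is then censored for a possibly outcome-related reason, and DOR may be censored at a date that no scan supports.

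The documents give no frequency, so the size across the trial cannot be estimated. The day counts above are one-subject illustrations that rest on the assumed dates and cutoffs, on nominal visit timing and, for DOR, on the subject being recorded as alive. PFS and DOR are exploratory and pre-withdrawal data are kept. The effect on the primary ORR is likely small, and I put no figure on it. This is a wording correction worth making and does not challenge the design or its decision rule.

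**What to change.** - **Protocol 9.12:** in place of withdrawal from the trial, write *discontinued from tipifarnib; tumor assessments and survival follow-up continue per Sections 8.1 and 11.7*. Section 8.4 can stay as it is.
- **SAP 9.2:** censor DOR for responders without documented progression at the last evaluable tumor assessment, not at the analysis cutoff date. In the example, a subject still lost to scanning would then contribute 29 censored days, not 315 or 680.

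The cost is one phrase in the protocol and one sentence in the SAP. The scans are already required, so no procedure is added. If follow-up has already ended, the SAP change can still be made before the database is frozen, and the discontinuation reasons tabulated under SAP 8.1 should help show how many subjects are affected. An ORR among all treated subjects would be a reasonable general sensitivity analysis but is not needed for this point.

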9.13 Dietary or Other Protocol Restrictions

No dietary restrictions related to tipifarnib are required. Subjects will be instructed to administer their dose of tipifarnib with a meal as the presence of food has been shown to improve the absorption of tipifarnib, as well as to reduce variability in the pharmacokinetic profile.

Tablets should be swallowed whole with water (~8 oz. or 250 mL). Tablets may be chewed or crushed if the Investigator deems it necessary. Use of a percutaneous endoscopic gastrostomy tube or nasogastric tube is allowed at the judgment of the Investigator.

Unless otherwise contraindicated, subjects should be advised to be appropriately hydrated during the course of the study (e.g. drinking at least 8 glasses of water/day).

9.14 Potential Effects on Reproduction and Development

Male and female fertility and reproductive capacity has been shown to be impaired in rats and additional details can be found in the Tipifarnib Investigator's Brochure.

In light of the observations in nonclinical testing, both female subjects and male subjects with female partners of child-bearing potential must agree to use a highly effective method of contraception for 2 weeks prior to screening, during, and at least 4 weeks after last dose of trial

medication. Female subjects of child-bearing potential must have a negative serum or urine pregnancy test within 72 hours prior to start of trial medication.

Additionally, since tipifarnib could induce toxicity of male reproductive organs and cause impairment of fertility, sperm cryopreservation should be recommended for male subjects wishing to preserve their fertility following tipifarnib treatment. Additionally, if the participant in the study is male, then the following items will be discussed with the subject:

- Prevention of pregnancy in a female partner
- Prevention of exposure of a partner to semen by any means (not just intercourse)
- Prevention of the possible exposure of a pregnant female to the study drug from semen.
- Informing their partner of the potential for harm to an unborn baby. The partner should know that if pregnancy occurs, she should promptly notify her personal doctor.
- Acceptable methods of birth control for male subjects while participating in this study and for 4 weeks after the last dose of the study drug:
 - o Abstinence (no sex)
 - o Condom plus spermicidal agent (foam gel/cream/film/suppository)

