7 SUBJECT SELECTION

7.1 Inclusion Criteria

For inclusion of a subject in the study, all of the following inclusion criteria must be fulfilled:

- 1. Subject is at least 18 years of age.
- 2. Subject has a histologically or cytologically confirmed diagnosis of non-hematological malignancy for which there is no curative therapy available. *In addition, in France and Korea, Republic of, subject must have a malignancy that has relapsed or is considered treatment failure to standard of care therapy in a multidisciplinary clinical staff meeting.*
 - a. Cohort 1 will enroll subjects with malignant thyroid tumors with HRAS mutations, independently of thyroid histology.
 - b. Subjects with non-hematological HRAS mutant tumors (except malignant thyroid tumors) who met eligibility criteria were enrolled in the first stage of Cohort 2 (completed). Subjects must have HNSCC with HRAS mutations in order to be enrolled in the second stage of Cohort 2 and its extension.
 - c. Cohort 3 will enroll subjects with SCCs with HRAS mutations other than HNSCC, independently of tissue origin. Subjects with mucosal HNSCC with skin involvement will be enrolled in cohort 2 whereas subjects with primary skin SCC located in the head and neck will be enrolled in cohort 3.
- 3. Subject has a tumor that carries a missense HRAS mutation with a VAF ≥ 20% according to Next Generation Sequencing or any other methodology approved by the Sponsor. HRAS status may have been assessed either in primary tumor tissue, recurrent or metastatic disease.
- 4. Subject has consented to provide at least 10 unstained tumor slides (or equivalent tumor tissue blocks) for retrospective testing of HRAS gene tumor status, including T81C polymorphism, except in cases of anaplastic thyroid cancer. Provision of tumor slides is not required for cases of anaplastic thyroid cancer.
- 5. Subject has measurable disease according to RECIST v1.1 and has relapsed or is refractory to prior therapy.
- 6. At least 2 weeks since the last systemic therapy regimen prior to enrolment. Subjects must have recovered to NCI CTCAE v. 4.03 < Grade 2 from all acute toxicities (excluding Grade 2 toxicity that are not considered a safety risk by the Sponsor and Investigator) or toxicity must be deemed irreversible by the Investigator.

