- 7. At least 2 weeks since last radiotherapy. If radiation was localized to the only site of measurable disease, there must be documentation of disease progression of the irradiated site. Subjects must have recovered from all acute toxicities from radiotherapy.

- 8. ECOG performance status of 0 or 1
- 9. Acceptable liver function:
 - a. Bilirubin $\leq 1.5 \times ULN$.
 - b. AST (SGOT) and ALT (SGPT) $\leq 1.5 \text{ x ULN}$.
- 10. Acceptable renal function with serum creatinine $\leq 1.5 \text{ x ULN}$ or a calculated creatinine clearance $\geq 60 \text{ mL/min}$ using the Cockcroft-Gault, CKD-EPI or MDRD formulas.
- 11. Acceptable hematologic status:
 - a. ANC $\geq 1000 \text{ cells/}\mu\text{L}$.
 - b. Platelet count $\geq 75,000/\mu L$.
 - c. Hemoglobin $\geq 8.0 \text{ g/dL}$.
- 12. Serum albumin \geq 3.5 g/dL. Subjects with tumors potentially highly sensitive to tipifarnib (HRAS mutant VAF \geq 35%) may be enrolled despite a serum albumin \leq 3.5 g/dL.
- 13. Female subjects must be:
 - a. Of non-child-bearing potential (surgically sterilized or at least 2 years post-menopausal);
 - b. If of child-bearing potential, subject must use a highly effective method of contraception, such as combined (estrogen and progestogen containing) hormonal contraception associated with inhibition of ovulation, progestogen-only hormonal contraception associated with inhibition of ovulation, intrauterine device, intrauterine hormone-releasing system, bilateral tubal occlusion, vasectomised partner or sexual abstinence. Both females and male subjects with female partners of child-bearing potential must agree to use a highly effective method of contraception for 2 weeks prior to screening, during, and at least 28 days after last dose of trial medication for females and 90 days for males. Female subjects must have a negative serum or urine pregnancy test within 72 hours prior to start of trial medication.
 - c. Not breast feeding at any time during the study.
- 14. Written and voluntary informed consent understood, signed and dated.

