10.9 Adverse Event Reporting Period

The adverse event reporting period for safety surveillance begins when the subject is included into the trial (date of first signature of informed consent) and continues through the trial's post-treatment follow-up period, defined as 30 days from the final administration of the trial treatment or immediately before initiation of any other anticancer therapy, whichever comes first.

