10.13 Pregnancy and In Utero Drug Exposure

Only pregnancies considered by the Investigator as related to trial treatment (e.g., resulting from a drug interaction with a contraceptive medication) are considered as adverse events. However, all pregnancies with an estimated conception date during the study safety period must be recorded by convention in the AE page/section of the e-CRF. The same rule applies to pregnancies in female subjects and in female partners of male subjects. The Investigator must notify the Sponsor in an expedited manner of any pregnancy using the Pregnancy Report Form, which must be transmitted according to the same process as described for SAE reporting.

Investigators must actively follow up, document and report on the outcome of all these pregnancies, even if the subjects are withdrawn from the trial. The Investigator must notify the Sponsor of these outcomes using the Pregnancy Report Form, and in case of abnormal outcome, the Adverse Event Report Form when the subject sustains an event and the Parent-Child/Fetus Report Form when the child/fetus sustains an event.

Any abnormal outcome must be reported in an expedited manner, while normal outcomes must be reported within 45 days from delivery.

In the event of a pregnancy in a subject occurring during the course of the trial, the subject must be discontinued from trial medication immediately. The Sponsor must be notified without delay and the subject must be followed as mentioned above.

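### Section 9.14 tells male subjects to use contraception for 4 weeks after the last dose; inclusion criterion 13b requires 90 days, which is 62 days longer

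*Protocol*

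**What the plan says.** The period for which men must use contraception after treatment appears in two parts of the Protocol.

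- **Inclusion criterion 13b**, worded the same way on this point in the Synopsis and in Section 7.1, requires highly effective contraception for "at least 28 days after last dose of trial medication for females and 90 days for males". The lead sentence of Section 7.1 makes it binding at entry: "all of the following inclusion criteria must be fulfilled". The male requirement sits inside a criterion whose heading is about female subjects.
- **Section 9.14**, general sentence: "both female subjects and male subjects with female partners of child-bearing potential must agree to use a highly effective method of contraception", with a post-treatment period of "at least 4 weeks after last dose of trial" medication. Both sexes get the same period.
- **Section 9.14**, list of items to be discussed when the participant is male: the item on acceptable birth control methods applies during the study "and for 4 weeks after the last dose of the study drug". It is not expressed as a minimum and does not point to 13b.

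Two other sections bear on what would be recorded if a partner became pregnant. Section 10.13 says that "all pregnancies with an estimated conception date during the study safety period must be recorded by convention", and applies this to female partners of male subjects, but does not define the study safety period. Section 10.9 ends the adverse event reporting period with a post-treatment follow-up "defined as 30 days from the final administration of the trial treatment", or earlier if another anticancer therapy is started.

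**The concern.** Section 9.14 is the Protocol's dedicated section on reproductive risk, and its list is a required discussion with every male subject. It is therefore a natural text for site staff to counsel from. The 90-day rule is easier to miss, because it stands under a heading about women and takes effect only after the last dose, long after eligibility was checked.

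The instruction concerns exposure of a partner and a possible fetus. Section 9.14 itself reports impaired fertility and reproductive capacity in rats, warns of possible toxicity to male reproductive organs, and asks that partners be told of possible harm to an unborn baby. If the shorter period is the one passed on, men may stop while 13b still expects them to continue.

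**Working it through.** The plan gives no calculated figure here, so the check compares the texts and converts units.

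**Inputs**

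| Source | Female period | Male period |
|---|---|---|
| Criterion 13b (Synopsis, Section 7.1) | at least 28 days | 90 days |
| Section 9.14, general sentence | at least 4 weeks | at least 4 weeks |
| Section 9.14, male discussion list | not applicable | 4 weeks |

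**Step 1. Common units.** 4 weeks × 7 = 28 days.

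**Step 2. Females.** 28 − 28 = 0 days. The two sections agree.

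**Step 3. Males.** 90 − 28 = 62 days. These are days 29 to 90 after the last dose. Criterion 13b covers them; the male item in Section 9.14 does not.

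**Step 4. Can both texts be met?** Yes. A man who continues to day 90 meets 13b, the general sentence and the list item. The reverse fails: a man who stops on day 29 has done all that Section 9.14 asks and has not met 13b.

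**Step 5. Would pregnancy recording catch the difference?** This depends on what Section 10.13 means by the study safety period. *Assumption:* it is the reporting period of Section 10.9, which runs to at most 30 days after the last dose. Then 90 − 30 = 60 days (days 31 to 90) fall outside required recording, so at least 60 of the 62 days have no such backstop. If the sponsor defines the period differently, this figure changes.

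**Step 6. After correction.** With 90 days for males in Section 9.14, the difference is 90 − 90 = 0 days. The female period stays at 28 days in both places.

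**The case against.** The best reply is that the conflict is narrow. The general sentence in Section 9.14 sets a floor, and 90 days satisfies it. Criterion 13b is the stricter, sex-specific rule; it reads the same in both places and binds every man enrolled. That leaves one list item, which is mainly about methods and mentions the period in passing. It does not waive the agreement given under 13b. **This stands as a description of scope:** the general sentence is compatible but less specific, and the list item is the real problem. It does not remove the problem, because the item belongs to a required discussion and states the shorter period flatly.

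A second reply is that no harm has been shown. Section 5.1.1 gives a terminal half-life of about 19 hours and reversal of enzyme inhibition within 3 to 7 days, so the documents do not show drug persisting on days 29 to 90. The consent form could not be seen, and nothing can be inferred from its absence. **This also stands in part.** The documents do not establish which period is pharmacologically needed, and the half-life does not settle the question for effects on male germ cells. The point is that two current instructions differ, not that 90 days has been proved necessary.

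A third reply is that the recording gap in Sections 10.9 and 10.13 is a separate matter. It rests on an assumed definition, it would exist even if Section 9.14 already said 90 days, and correcting Section 9.14 would not close it. **That is correct.** The gap is relevant here only because it means the Protocol may lack a backstop for the inconsistency.

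**Conclusion.** The concern holds: Section 9.14 is wrong as written for male subjects. The discussion item gives a post-treatment period 62 days shorter than criterion 13b, and the general sentence applies the female figure to both sexes. Since 13b separates the sexes explicitly and does so in two places, its 90 days looks deliberate, and Section 9.14 is the text to bring into line.

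The 62 days follows directly from the two texts and needs no assumption. The figure of 60 days without required pregnancy recording depends on reading the study safety period as the Section 10.9 period. The number of men affected cannot be estimated: up to 75 evaluable subjects are planned, with no sex split or partner status given. What men are actually told is unknown without the consent form.

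**What to change.** In Section 9.14, change the general sentence to at least 4 weeks (28 days) after the last dose for females and at least 90 days for males. In the male discussion list, replace the 4-week period with at least 90 days and refer to criterion 13b. Amend 13b instead only if the sponsor's safety function documents that a shorter male period is correct. Check that the consent form carries the same period.

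The cost is a wording correction to two sentences in one section and a consent-form check. Sample size, endpoints and analyses do not change. These edits do not settle how far pregnancy recording extends after the last dose; that would need a definition of the study safety period in Section 10.13.
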